Development of a Behavioral Intervention for Chronic Pain in Individuals With HIV
NCT02824562

STUDY PROTOCOL

Version 1.0
Sep, 2017

Send Questions or Comments to:
[name] [contact]
[name] [contact]

I. STUDY OVERVIEW

Defined as pain lasting longer than three months, chronic pain affects up to 30% of the US population. It often occurs in patients with complex chronic illness, including medical, psychiatric, and substance use comorbidities. However, chronic pain is not simply a symptom of these comorbidities. Its distinct neurobiologic basis and substantial impact on physical and emotional function make it a serious illness in itself. In recognition of its importance, the Institute of Medicine has called chronic pain a “public health crisis,” and identified research on chronic pain, particularly in populations most burdened by this condition, to be a priority.

The burden of chronic pain in HIV-infected patients is substantial. Prevalence estimates of chronic pain in HIV-infected patients are as high as 39-85%. Mounting evidence suggests that chronic pain in HIV is often associated with psychiatric illness, especially mood disorders such as depression, and has serious health consequences, including up to 10 times greater odds of functional impairment.

Non-pharmacologic, behavioral interventions to decrease pain and improve physical and emotional function in HIV-infected patients with chronic pain are needed. A consensus panel identified pain, physical, and emotional function to be the most important outcomes of chronic pain interventions. Commonly used pharmacologic therapies, including opioids, often do not result in substantial improvement in these outcomes, and carry risks including misuse, abuse, and addiction. In HIV, opioids may

actually be associated with worse pain, and adversely interact with antiretrovirals. Behavioral interventions are among the most effective and safe non-pharmacologic treatments for chronic pain in the general medical population.

II. OBJECTIVES

In this study we will conduct a two-arm pilot randomized controlled trial of the chronic pain behavioral intervention to investigate feasibility, acceptability, and when possible, preliminary impact.

III. STUDY ACTIVITIES

a) STUDY POPULATION

A total of 40 patients (up to 60) who are patients at the UAB 1917 clinic, enrolled in CNICS, experiencing chronic pain (Brief Chronic Pain Screening Questionnaire (BCPQ) = at least moderate pain for at least 3 months) and moderately severe and impairing chronic pain (PEG pain questionnaire = average of all three times is 4 or greater).

Inclusion Criteria

1. Enrolled in CNICS
2. Age \geq 18 years
3. Chronic pain (Brief Chronic Pain Screening Questionnaire (BCPQ) = at least moderate pain for at least 3 months)
4. Moderately severe and impairing chronic pain (PEG pain questionnaire = average of all three times is 4 or greater)

Exclusion Criteria

1. Do not speak or understand English
2. Are planning a new pain treatment like surgery

3. Cannot attend the group sessions

Recruitment of participants will take place in the 1917 clinic. Participants will be recruited via word-of-mouth by clinic staff or providers, calls generated from flyer tear-offs, and responses to the flyer on the TV monitors.

b) PRE-SCREENING

Potential participants will be prescreened over the phone using our prescreening phone script. If the individual passes the telephone prescreen, he or she will be scheduled for an in-person pre-screening visit by a member of the STOMP recruitment team. The date and time of the pre-screening visit along with the participant contact information and preferred method of contact will be recorded on the Prescreening Visit Appointment Form. About 48 hours prior to the in-person prescreen visit, a reminder call from the research staff will be made to remind the potential participant of the prescreening visit. On the day of the prescreen, the research staff member conducting the prescreen will log onto Redcap and establish a unique RedCap instance for this participant and complete the prescreen section only. At the end of the prescreen, the research tech will record the participant's eligibility on the Prescreening Visit Appointment Form. If the participant is eligible for enrollment, a Screening and Enrollment Visit will be scheduled and recorded on a Screening and Enrollment Visit form. The participant will also be thanked and given their \$25 incentive.

If the participant is not eligible, he or she will be thanked for their time and give their \$25 incentive.

c) SCREENING AND ENROLLMENT

The Screening and Enrollment Visit will be scheduled approximately 2-4 weeks from the date of the pre-screen visit and recorded on a Screening and Enrollment Visit form. Participants will receive a reminder call at about a week and 48 hours prior to the scheduled screening visit. At the beginning of the screening and enrollment visit, the participant will complete the informed consent process.

Informed Consent Procedures

Informed consent will be administered by staff trained in accordance to the University of Alabama at Birmingham Institutional Review Boards guidelines for obtaining informed consent. The staff member obtaining consent must verify the following: protocol name, version number, dates for use, and institution. The Study team member will also ensure that the most recent informed consent is being used for the study. Initial informed consent must be completed and documented before any other study related procedures are done.

Comprehension will be assessed by asking the participant to summarize the study activities or some general open ended questions will be asked like what can you tell me about this study, can you tell me about how long the study may last, etc.

The consent process is estimated to take around 30 minutes.

Study staff will ensure that the participant has signed and dated the consent form including the HIPAA form.

All signed consent forms will be stored in locked file cabinets under respective participant files.

Baseline Assessment

The research staff will then administer the baseline assessment which includes a confirmatory set of screening questions via RedCap. Confirmation of the participant's eligibility will be recorded in RedCap.

Following completion of the baseline assessment, participants will be thanked for coming and given their \$50 incentive payment for their time. Completion of Baseline assessment will be recorded in excel logs.

d) RANDOMIZATION

Our team will utilize a 1:1 ratio for allocation to the treatment and control arms at each participating site. The UAB statistician will generate a list of random arm assignments for each site. Randomization list will be provided to the study coordinator to create sealed envelopes with participant ids on it in chronological order.

Once the participant completes the enrollment procedures, study staff will open the sealed envelope and will show the random arm assignment to participant and record it in the excel logs.

e) ASSIGNMENT OF ARM OF STUDY

Approximately, 20 intervention arm and 20 control (standard of care) participants will be randomly assigned. Recruiting staff and research personnel will be masked to treatment arm assignment at the initial study visit. After the initial study visit, study coordinator will inform the participant of the follow-up assessments and thank the participant for their time. Staff personnel doing the assessment will still be blinded to the arm assignment.

If the participant is randomized to the intervention group, the participant will be informed of the next steps which includes the first group session. If the date of the first group

session has been established, the participant will be informed of the date and time. If it has not been scheduled, the participant will be informed that s/he will receive a call within the next two weeks informing his/her with the date and the time of the first group session

f) INTERVENTION

This behavioral intervention consists of 12 intervention sessions (6 group and 6 individual sessions). The sessions will be completed over a period of 12-16 weeks from enrollment. The first intervention session will be a group session for all participants followed by individual and then alternating group and individual session for the rest of the sessions.

Group intervention Sessions

A total of 6 group sessions will be conducted over a period of 12-16 weeks from study enrollment date. These sessions will be led by a peer. A peer is an HIV-infected patient of the UAB 1917 Clinic living with chronic pain, who has completed all ten of the one-on-one sessions offered, received training to co-facilitate the six group sessions with the interventionist, and is successfully self-managing his/her chronic pain.

Participants will receive a reminder call/text approximately 48 hours before the group session to remind them of the upcoming session. Participants will also be notified of the upcoming group sessions at the end of each one-on-one intervention. Group sessions will be conducted in UAB 1917 clinic building or the Bevill Biomedical Research Building (BBRB). A sign-in sheet will be used to document attendance. Session notes will be used to document any major issues presented or any anecdotal nuances identified. The date, start time and end time of the session will also be documented. Participants will

complete an anonymous session feedback form at the end of each session. Each session will be audio recorded and transcribed later using a third party.

Individual Intervention Sessions

A total of 6 individual sessions will be conducted over a period of 12-16 weeks from study enrollment date.

Each individual intervention session will be scheduled by the staff interventions preferably prior to next group session. The intervention date and time will be recorded on the Individual Intervention Session Form along with the intervention no. and topic. The participant will receive a reminder communication about the upcoming session approximately 48 hours before the session. An Intervention Session Form will be used to record the date, time, length of session, topic covered, homework, next steps, and any nuances identified during the session. An adverse event form will be completed if any physical, social or psychological issues arise a result of participating in this study and warrant immediate attention. The date of the next group session will be announced and the date of the next one-on-one session will be recorded at the bottom of the Intervention Session Form. Participants will complete an anonymous session feedback form at the end of each session. Each session will be audio recorded and later transcribed using a third party.

Each session will be reviewed by a member of the research team not participating in the session for fidelity using the fidelity checklist.

Reminder calls

Study staff will conduct up to 5 reminder calls to remind about their upcoming intervention session. Please note the purpose of these calls is to remind about

appointments but in case patient initiates the conversation regarding intervention or other related to the study staff will talk to participant regarding intervention.

If a participant misses a session, they will receive up to 5 reminder calls asking why and what we can do to help. If there are things we can do to help that are reasonable (e.g., more reminders, more transportation assistance, or other things), we will provide them.

If they miss more than one visit, they may receive a call asking about their future participation in the study and whether, if they are unwilling to participate in intervention sessions, they would willing to just complete outcome assessments.

Assessments

All participants in the intervention group will also receive a baseline, post-intervention (after all sessions are completed), and at about 3 months (1 month leeway) assessment. These may be conducted by phone or in person. They will also participate in an audio-recorded in –person qualitative interview at the mid-point and end of the trial which will be transcribed using a third party company.

Qualitative interviews

Participants assigned to intervention arm, peers and interventionists of the study will be interviewed at mid-point of the study and end of the study to provide their feedback on the STOMP intervention. These interviews will be audio-recorded and later transcribed using third party.

g) CONTROL

The control group will receive “treatment as usual”. The “treatment as usual” or control arm refers to the standard of care that patients receive at the UAB 1917 clinic. This standard of care is for patients to discuss chronic pain with their providers at their

discretion. Although highly variable, providers can recommend and prescribe pharmacologic (e.g., opioid and other pain medication), non-pharmacologic (e.g., physical therapy, referral to psychology) approaches for pain. This study will not interfere in any way with usual care. No additional treatment will be provided to participants allocated to the control group. The control group participants will complete the baseline assessment and around 12 week follow-up (1 month leeway) assessment.

h) SNAP SHOT OF STUDY ACTIVITIES

Procedure	Length of Time Required of Participants	Frequency of Repetition
Individual sessions (intervention group only)	6 sessions, up to approx. 120 minutes each	Maximum of on average every other week
Group sessions (intervention group only)	6 sessions, up to 120 approx minutes each	Maximum of on average every other week
Questionnaire assessments – see attached	Approx 30 minutes	Baseline, end of intervention, and 3 months after intervention
Qualitative interviews (intervention group only)	Approx up to 120 minutes	Midpoint and end of trial
Phone calls (intervention group only)	Approx up to 30 minutes	Average of once weekly

h) SUMMARY OF COMPENSATION

Intervention group

In person for Prescreen	\$25
Screening/Enrolment visit	\$50
Mid-point qualitative interview	\$50
End of study qualitative interview	\$50
Post intervention follow up	\$50
3 month follow up	\$100

Control group

In person for Prescreen	\$25
Screening/Enrolment visit	\$50
12 week assessment	\$50
3 month follow up	\$100

Offer parking vouchers/coffee vouchers/bus tickets etc. as required to the participants if that is the standard practice followed over at the clinic.

IV. DATA COLLECTION AND MANAGEMENT

All study documentation will be kept in locked file cabinets in BBRB or CCB in study personnel's offices. RedCap database can only be accessed by STOMP personnel using a UAB computer or encrypted laptop.

V. DATA ANALYSIS

Outcomes were reported as means and standard deviations for continuous variables, and frequencies and percentages for categorical variables. T-tests were used to compare change scores for continuous variables and Fisher's exact

tests were used to compare percentages. Interviews were analyzed thematically by two independent coders. Discrepancies were reconciled, a code book was created, and the lead analyst coded the remaining transcripts with continued input from the other coder. Representative quotes are presented for themes that helped us understand why and how the intervention could work.

VI. CRISIS PROTOCOL

As a general note, referrals can be made for crisis consultation at any time. The research staff will document the findings of his/her evaluation and the course of action taken. Providers for the patient may be informed about the same.

VII. PROTECTION OF HUMAN SUBJECTS

Our team has devised a comprehensive plan for ensuring protection of human subjects throughout the course of the proposed study. We will utilize an English-language consent form with common phrasing that describes that no special privileges or considerations will be conferred as a result of study participation, and that access to medical care will not be affected by the potential participant's decision to enroll in the study. The procedures listed in the following sections detail procedures that have been approved and utilized during recent years of clinical and behavioral trials at each site for collaborative research that utilizes sensitive information from participants. Our team will make every effort to protect all participants' confidential and private information in order to minimize possible study-associated risks.

All findings related to this research will be available and provided to study participants in accordance with standard practices. Clinical and measurement data used for research studies will be released only in de-identified fashion.

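### The PEG comparison is planned as an unadjusted change-score t-test and makes no use of the second pre-randomisation PEG reading that the screening steps imply, so it is less precise than the collected data appear to allow

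*Combined protocol and SAP*

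**What the plan says.** All references are to the combined protocol and SAP.

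- **Eligibility (III.a).** Participants must have "moderately severe and impairing chronic pain (PEG pain questionnaire = average of all three times is 4 or greater".
- **Prescreen (III.b).** At the in-person visit, staff "establish a unique RedCap instance for this participant and complete the prescreen section only". Then: "At the end of the prescreen, the research tech will record the participant's eligibility on the Prescreening Visit Appointment Form".
- **Interval (III.c).** "The Screening and Enrollment Visit will be scheduled approximately 2-4 weeks from the date of the pre-screen visit".
- **Consent (III.c).** "At the beginning of the screening and enrollment visit, the participant will complete the informed consent process". The prescreen answers therefore precede consent.
- **Baseline (III.c).** "The research staff will then administer the baseline assessment which includes a confirmatory set of screening questions via RedCap". Confirmed eligibility is then entered in RedCap.
- **Randomisation (III.d).** "Once the participant completes the enrollment procedures, study staff will open the sealed envelope". Both screening steps come before allocation.
- **Analysis (V).** "T-tests were used to compare change scores for continuous variables". The section does not say which reading is the baseline, names no outcome instrument and includes no covariate.

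The table of study activities (III.h) refers to an attachment for the questionnaires. Whether PEG is among the follow-up instruments cannot be read from the text.

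**The concern.** A staff member can hardly record eligibility at the prescreen, or confirm it at baseline, without a PEG score, because a PEG threshold is one of the inclusion criteria. Each randomised participant should then have two readings taken before allocation.

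A t-test on change scores ordinarily subtracts one reading with a fixed weight of 1. That is inefficient in two ways. It lets noise in the single baseline pass fully into the outcome, where regression would scale it down. It also makes no use of any further information in the other reading.

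With about 20 participants per arm, imprecision is the main limit on any early estimate of effect. Because two candidate values appear to exist, an undefined baseline also leaves a choice to the analyst after the data are seen.

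**Working it through.** **Inputs from the documents.** About 20 per arm (III.e), so N = 40; PEG cut-off 4 (III.a); two screening steps 2-4 weeks apart, both before the envelope is opened (III.b to III.d). The documents give no SD, correlation, alpha or power, so there is no planned figure to reproduce.

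**Assumptions.** PEG is scored at both visits and at follow-up. Scores lie on 0-10 with SD 2 and mean 5.5 or 6.5, and both early readings must be at least 4. Before the cut-off is applied, the prescreen-baseline correlation r12 is 0.6-0.8, and the correlations with follow-up (r1 for prescreen, r2 for baseline visit) are 0.5-0.7. The prescreen is further from follow-up, so only settings with r1 no larger than r2 are counted.

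**Formulas without the cut-off, in units of SD²**

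- Change from one baseline: 2(1 − r2)
- Change from the mean of two: 1 + (1 + r12)/2 − (r1 + r2)
- ANCOVA on one baseline: 1 − r2²
- ANCOVA on both readings: 1 − (r1² + r2² − 2·r1·r2·r12)/(1 − r12²)

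*All correlations 0.5.* Planned change score: 2(0.5) = 1.00. ANCOVA on one baseline: 1 − 0.25 = 0.75. ANCOVA on both: 1 − (0.25 + 0.25 − 0.25)/0.75 = 0.667. With 20 per arm, two-sided alpha 0.05 and 80% power, the detectable difference is 2.80·√(variance·2/20), or 0.89, 0.77 and 0.72 SD respectively. Power for a 0.5 SD effect is about 35%, 45% and 49%.

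*r12 = 0.7, r2 = 0.6, r1 = 0.5.* Planned change score: 0.80. ANCOVA on one baseline: 0.64, ratio 0.80. ANCOVA on both: 1 − (0.25 + 0.36 − 0.42)/0.51 = 0.627, ratio 0.78. Change from the mean: 1 + 0.85 − 1.1 = 0.75, ratio 0.94. With r1 = 0.40, change from the mean becomes 0.85, ratio 1.06, which is worse than the planned score.

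**Simulation with the cut-off.** Trivariate normal scores were clipped to 0-10 and kept if both early readings were at least 4. ANCOVA variances were multiplied by (N − 3)/(N − k − 3) for k covariates, to allow for estimating the slopes at N = 40: 37/36 = 1.028 for one and 37/35 = 1.057 for two. Selected settings:

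| Mean | r12 | r1 | r2 | One-baseline ANCOVA ÷ planned | Two-covariate ANCOVA ÷ planned | Two ÷ one | Change from mean ÷ planned |
|---|---|---|---|---|---|---|---|
| 6.5 | 0.6 | 0.7 | 0.7 | 0.879 | 0.725 | 0.825 | 0.700 |
| 5.5 | 0.7 | 0.6 | 0.6 | 0.873 | 0.829 | 0.949 | 0.833 |
| 5.5 | 0.7 | 0.5 | 0.6 | 0.890 | 0.902 | 1.013 | 0.943 |
| 5.5 | 0.7 | 0.5 | 0.7 | 0.936 | 0.963 | 1.028 | 1.073 |
| 5.5 | 0.8 | 0.5 | 0.7 | 0.950 | 0.962 | 1.013 | 1.156 |

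**Ranges over all settings counted**

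- Two-covariate ANCOVA against the planned test: 0.725 to 0.963, a cut of about 4-27%. In effective numbers, 40/0.963 = 41.5 to 40/0.725 = 55.2. The standard error falls by 1 − √0.963 = 2% to 1 − √0.725 = 15%.
- One-baseline ANCOVA against the planned test: 0.816 to 0.950, a cut of 5-18%.
- Contribution of the second reading over one-baseline ANCOVA: 0.825 to 1.028, from an 18% gain to a 3% loss.
- Subtracting the simple mean: from a 30% cut to a 16% increase. The mean as a single covariate can be up to 16% worse than the baseline-visit score alone.

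**The case against.** The strongest reply is that the central fact is inferred. PEG is named at neither visit, the repeat screening items are not listed, and the follow-up questionnaires are in an attachment. A reader might infer that the plan takes PEG twice and deliberately throws one reading away. The documents do not support that: section V is silent on which reading, or combination of readings, forms the baseline. This part of the reply stands, and it is why the point is conditional.

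A second reply is that the extra reading may add little. This stands in part. Where the prescreen predicts follow-up less well than the baseline visit, the second covariate can cost up to about 3%, and one-baseline ANCOVA already captures the available gain. It is also tempting to infer that averaging the two readings must reduce noise. That fails for the same reason: a fixed equal weight can increase the variance. Separate covariates avoid this because the data set the weights.

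Third, the prescreen precedes consent, and III.c requires consent before other study procedures. Use of those answers in the analysis has to be covered by the consent and may need ethics review.

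Finally, this is a pilot with no power target, and section II makes early effect secondary to feasibility and acceptability. That limits the importance of the point, but does not make an unadjusted change score the better choice.

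**Conclusion.** The point holds as a minor gain in precision. Two pre-randomisation PEG readings are strongly implied, and the planned t-test uses neither regression adjustment nor, as far as the text shows, the second reading. In every setting examined, ANCOVA on both readings had lower variance than the planned change score, by about 4-27% at N = 40. Much of that can come from adjusting for one baseline alone.

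The size depends on correlations, a mean and an SD that the documents do not give, and on PEG being repeated at follow-up. A reader might also infer a bias between arms. There is none from this source: both readings precede allocation, so the cut-off and any regression to the mean affect the arms alike in expectation. No decision rule in the plan depends on the result.

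**What to change.** Add to section V, for PEG if it is a follow-up outcome:

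- Compare follow-up PEG between arms by ANCOVA, with the baseline-visit PEG and the prescreen PEG as separate covariates, where the prescreen score is recorded and its use is covered by consent.
- Otherwise adjust for the baseline-visit PEG alone.
- Report the change-score t-test, with change defined from the baseline visit, as a sensitivity analysis.
- Do not prescribe the simple mean of the two readings, either as the value subtracted or as a single covariate.

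The cost is a few lines in section V, a line in the consent form covering the prescreen answers, and one degree of freedom beyond single-baseline adjustment (two beyond the t-test). No visit, question or participant is added. Section V is written in the past tense; if the outcome data have already been examined, the ANCOVA should be labelled as added afterwards.

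### The adverse event form is limited to study-attributed, urgent issues and is named only for intervention-arm individual sessions, so its counts would be incomplete and not comparable between arms

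*Combined protocol and SAP*

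**What the plan says.** The adverse event form appears once, in section III.f under Individual Intervention Sessions: "adverse event form will be completed if any physical, social or psychological issues arise a result of participating in this study and warrant immediate attention". In section III.h, the activity table marks these sessions for one arm only: "Individual sessions (intervention group only").

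For the group sessions, the same section names a different record: "Session notes will be used to document any major issues presented or any anecdotal nuances identified".

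For the control arm, section III.g says: "The control group participants will complete the baseline assessment and around 12 week follow-up (1 month leeway) assessment". The control-group compensation list adds a payment for a "3 month follow up". Neither place describes an enquiry about harms.

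Section VI is not restricted by arm. It states: "As a general note, referrals can be made for crisis consultation at any time". It continues: "The research staff will document the findings of his/her evaluation and the course of action taken".

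The objectives in section II are feasibility, acceptability and, where possible, an early look at effect. Section V plans no tabulation of adverse events.

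**The concern.** The protocol states a rule for recording harms, so this is not merely an omission. The rule uses relatedness and urgency to decide whether an event gets onto the form at all. Both are judgements better made after an event has been captured. Even perfect compliance leaves off the form a pain flare, distress or a social problem, such as unwanted disclosure in a group, if it is not urgent or nobody links it to the study.

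The rule is also attached to a type of contact that the control arm does not have. If form counts were later reported by arm, the intervention-arm figure would be too low as a count of problems, and the control-arm figure would reflect the lack of any described route to the form. These two faults can push a comparison in opposite directions. A low count could be read as reassurance, and an excess over controls as harm, when either might come from the recording rule. A pilot should also show the next trial whether harms can be measured in both arms, and this rule would not.

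**Working it through.** The documents give no adverse event rate, safety calculation or harms comparison, so there is no figure to reproduce. The check is of the text.

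**Step 1: the trigger.** Two yes/no conditions (arises from participation; warrants immediate attention) give 2 × 2 = 4 kinds of event.

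| | Immediate attention | No immediate attention |
|---|---|---|
| Attributed to participation | Form completed | Not on form |
| Not attributed | Not on form | Not on form |

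One of the four combinations reaches the form.

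**Step 2: where the form is named.**

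| Contact after randomisation | Arm | Record described | Form named? |
|---|---|---|---|
| 6 individual sessions (III.f) | Intervention | Session form, anonymous feedback, audio recording | Yes |
| 6 group sessions (III.f) | Intervention | Session notes, anonymous feedback, audio recording | No |
| Calls, about weekly (III.h) | Intervention | None stated | No |
| Qualitative interviews, mid-point and end (III.f) | Intervention | Audio recording, thematic analysis | No |
| Follow-up questionnaires (III.f, III.g, III.h) | Both | Attached questionnaires, not available to us | No |
| Crisis consultation (VI) | Not limited by arm | Findings and action taken | No |

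The form is therefore named for 6 of 6 + 6 = 12 intervention sessions. In the control arm it is named for none of the follow-up contacts. There is one such contact by section III.g, or two if the follow-up in the compensation list is included.

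**Step 3: do the other records fill the gap?** Session notes, session forms, interviews and crisis records can each document a problem, but none is a standard per-participant event count. Session feedback is anonymous, so it cannot be tied to a participant. The review of sessions by an uninvolved team member is for fidelity. A participant who misses more than one visit may be asked to complete outcome assessments only, and so would leave the one setting where the form is described.

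**Step 4: opportunity to detect.** The activity table lists "Phone calls (intervention group only") as a further one-arm contact. With sessions, calls and interviews all confined to one arm, problems have many more occasions to surface there. Events noticed during sessions could not be compared fairly with the control arm even under a broader trigger.

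**The case against.** The best defence is that the form is an escalation tool and not an outcome measure. Safety is not a stated objective, no harms comparison by arm is planned, and treating tolerability as part of acceptability is a reviewer's reading. This largely stands: the comparison problem matters only if counts are reported by arm. It does not rescue the form as a record of harms in the intervention arm, where the two entry conditions make it incomplete in any case.

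Several stronger readings are tempting and should be resisted.

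- A reader might infer that the control count must be zero. The trigger refers to study participation and names no arm. Controls are consented, randomised and assessed, and one could have an urgent problem arising from an assessment. The text supports only the statement that no procedure is described by which such an event would reach the form.
- A reader might infer that non-urgent harms go wholly unrecorded. The records in step 3, together with calls asking why a session was missed, are partial routes, though uncounted.
- A reader might infer that those delivering the intervention decide on attribution. The sentence is in the passive voice and does not say who decides.
- A reader might size the flaw by assuming an event rate and working out how many controls would have an event. That would count problems of any cause, whereas the form takes only related and urgent ones. A confidence limit for a zero count would reflect sample size and would remain after the fix.

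Finally, the attached questionnaires and one part of the protocol were not available, and section VII refers to later procedures that we have not seen. A harms item may exist there. If it does, it must be reconciled with the trigger in section III.f, which would still be too narrow as worded.

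**Conclusion.** The concern holds in a limited form. As described, the adverse event form captures only issues that are both attributed to participation and in need of immediate attention. It is named only for sessions that the intervention arm alone receives, and it has no described counterpart for controls. Counts from it would be incomplete in the intervention arm and not comparable between arms if reported.

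The size is structural: one of four kinds of event, half of the intervention sessions and no control-arm contact. No numerical bias can be stated, because the documents give neither an event rate nor the share of events that would meet the trigger. The conclusion assumes that the unavailable material does not already contain a harms enquiry common to both arms. The incompleteness in the intervention arm follows from the wording of the trigger; the lack of comparability has consequences only if counts by arm are reported.

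**What to change.** - **Trigger.** Reword section III.f so that the form is completed for any new or worsened physical, psychological or social problem reported at any group session, individual session, call or assessment. Record relatedness and urgency as fields on the form, and state who completes them. This changes recording only; the handling of urgent problems and crisis referral is untouched.
- **Common enquiry.** At the existing follow-up assessments in both arms, have the masked assessor ask one identical open question about such problems. Put it last and remind participants not to mention study sessions, so that outcome ratings are finished before any unmasking. Section III.g and the compensation list should first be reconciled on which follow-ups the control arm attends, so that the question falls at matching times.
- **Reporting.** Tabulate assessment-elicited events by randomised arm, descriptively. List session-detected events separately, because the intervention arm has more contacts.
- **If data collection is over**, as the past tense of section V may suggest, report form counts with the trigger stated and do not compare them between arms.

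The cost is one question in an assessment of about 30 minutes, a reworded trigger and one extra table. More minor events will be recorded, and a small risk of unmasking assessors remains.
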